8.2.4. Analyses of Other Endpoints

Demographics, alcohol and tobacco use, cardiovascular risk history, medical history, pretreatment and concomitant lipid-lowering medications, protocol deviations, compliance with study medication, exposure to study medication, and reasons for discontinuation from treatment and the study will be tabulated by treatment group according to sponsor standards.

The number and percent of subjects with randomized study drug dosing adjustments will be tabulated by treatment group at each visit, as well as at any time during the study. The number and percent of subjects at each dose and regimen will be tabulated by treatment group at each visit. The number and percent of subjects who maintained the dose and regimen from the previous visit and the number who changed the dose and regimen from the previous visit will be tabulated by treatment group for each post-baseline visit after the first visit.

Time from first dose of randomized study medication to premature discontinuation of randomized study medication will be analyzed in the SAS. The p-value from a log rank test stratified by geographic region and LDL-C at the pre-screening visit (<100 mg/dL, ≥100 mg/dL) will be presented. A Cox proportional hazards model will be fit with treatment group as a covariate and geographic region and LDL-C at the pre-screening visit (<100 mg/dL, ≥100 mg/dL) as stratification factors. The hazard ratio and a 95% CI will be presented.

Medication errors and subcutaneous injection site reaction assessments will be listed.

8.2.4.1. Pharmacokinetic/Pharmacodynamic/Immunogenicity Reporting

Only plasma samples for all bococizumab-treated subjects will be tested for immunogenicity; plasma samples for placebo-treated subjects will not be tested. Only ADA positive samples will be tested for nAb.

8.2.4.1.1. Definitions

ADA and nAb titers are provided to Pfizer in log₂ format and will be reported in the same manner. All titles and labels used in tables and figures should clearly indicate titer (log₂).

ADA Measurement Level Status:

An ADA measurement is considered as ADA positive if the ADA titer ≥ 6.23 ; otherwise if non-missing, the measurement is considered as ADA negative.

nAb Measurement Level Status:

An nAb measurement is considered as nAb positive if the nAb titer ≥ 1.58 (Assay #2). An nAb measurement is considered as nAb negative if the ADA measurement from that sample is negative or if the nAb titer < 1.58 .

ADA Subject Level Status – For subject level classification of ADA (positive, negative):

A subject will be considered ADA positive if:

- The subject is ADA negative at baseline and has at least 1 ADA positive post-dose measurement, or
- The subject is missing the baseline ADA measurement and has at least 1 ADA positive post-dose measurement, or
- The subject is ADA positive at baseline and has a >1.58 unit increase in ADA titer from a positive baseline titer in at least 1 post-dose measurement.

A subject will be considered ADA negative if:

- The subject is ADA negative at baseline and all post-dose measurements are negative, or
- The subject is missing the baseline ADA measurement and all post-dose measurements are negative, or
- The subject is ADA positive at baseline but does not experience >1.58 unit increase in titer from a positive baseline titer in any post-dose measurement.

nAb Subject Level Status – For subject level classification for nAb (positive or negative):

A subject will be considered nAb positive if:

- The subject is nAb negative at baseline and has at least 1 nAb positive post-dose measurement, or
- The subject is missing the baseline nAb measurement and has at least 1 nAb positive post-dose measurement, or

- The subject is nAb positive at baseline and has a >1.58 unit increase in nAb titer from a positive baseline titer in at least 1 post-dose measurement.

A subject will be considered nAb negative if:

- The subject is ADA negative, or
- The subject is nAb negative at baseline and all post-dose measurements are nAb negative, or
- The subject is nAb positive at baseline but does not experience a >1.58 unit increase in titer from a positive baseline titer in any post-dose measurement.

ADA (nAb) Response Type:

ADA (nAb) positive subjects will further be classified according to the type of ADA (nAb) response (treatment induced/treatment boosted/indeterminate):

A subject will be considered as having treatment induced ADAs (nAbs) if:

- The subject is ADA (nAb) negative at baseline with at least 1 ADA (nAb) positive post-dose measurement, or
- The subject's baseline ADA (nAb) sample is missing with an ADA (nAb) negative post-dose measurement followed by at least 1 ADA (nAb) positive post-dose measurement.

A subject will be considered as having indeterminate ADAs (nAbs) if:

- The subject's baseline ADA (nAb) sample is missing with at least 1 ADA (nAb) positive post-dose measurement that was not preceded by an ADA (nAb) negative post-dose sample.

A subject will be considered as having treatment boosted ADAs (nAbs) if:

- The subject's baseline sample was ADA (nAb) positive with an increase in ADA (nAb) titer of >1.58 unit increase in titer from a positive baseline titer in at least 1 post-dose measurement.

Timing of ADA (nAb) Positive Measurement:

ADA (nAb) positive subjects will also be classified according to the timing of the ADA (nAb) positive measurement with respect to last dose of bococizumab (on treatment/off treatment):

A subject will be considered as having on-treatment ADAs (nAbs) if:

- The subject has any ADA (nAb) detected within ≤ 14 days after last dose.

A subject will be considered as having off-treatment ADAs (nAbs) if:

- The subject has their first ADA (nAb) detected >14 days after last dose.

Duration of ADA (nAb) Response:

ADA (nAb) positive subjects will also be classified according to the duration of ADA (nAb) response (indeterminate/persistent/transient) if the date of the first post-baseline measurement to the date of the last post-baseline measurement is at least 16 weeks:

A subject will be considered as having indeterminate duration of ADAs (nAbs) if:

- The subject has a positive ADA (or nAb) detected at the last post-baseline time point only.

A subject will be considered as having persistent duration of ADA (nAb) if:

- The subject has positive ADA (or nAb) detected at all post-baseline samples assayed during any period of at least 16 weeks.

A subject will be considered as having transient duration of ADA (nAb) if:

- The subject has been classified as neither persistent nor indeterminate.

ADA (nAb) titer response:

Subjects will also be classified according to their maximum ADA (nAb) titer as

- ADA (nAb) negative,
- Maximum ADA (nAb) titer in the 1st tertile,
- Maximum ADA (nAb) titer in the 2nd tertile, or
- Maximum ADA (nAb) titer in the 3rd tertile.

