		
injury.
 
The requirements for anti-drug antibody blood sampling were modified so that anti-drug antibody measurements would be obtained for an injection site reaction that lasts more than 3 days.
 
Section 7.6, Triggered requirements was modified with the removal of the section describing the management of low-LDL-C with the concomitant dose modification paradigm, since this would happen automatically, through the IRT system and would not require direct study site involvement.
 
Section 7.6, Triggered requirements was modified with the removal of the section describing the management of positive ADAs, since the analysis of ADA is done in the laboratory and not at the study site.
 
Section 7.6, Triggered requirements was modified with the removal of the section requiring the site to seek approval from the medical monitor, to continue dispensing investigational product if the subject experiences unexplained muscle tenderness or weakness in the absence of a CK elevation, since there is no known relationship between PCSK9 inhibition and myopathy. While such symptoms are known to be related to statin administration, it is up to the investigator to follow local requirements for the administration of statins as described in the Section 5.8., concomitant medications.
 
In Safety Section 8.2, clarification was added that serious adverse event reporting includes the period between pre-screening and randomization.
 
Section 8.6.1 was modified to indicate that Protocol Specified Adverse Events were now to be described as Disease Related Efficacy Endpoints and that they would be identified by the Pfizer SAE triage group.
 
In Safety Section 8.14.1, Serious Adverse Event Reporting Requirements, the operations of an internal Pfizer Serious Adverse Event Triage Group are described, to improve the reporting of

--	--	---

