**Lipid, ADA, PK, and PCSK9 testing requirements after randomization:**

Lipid (direct LDL-C and lipid panel), ADA, PK, and PCSK9 testing, after randomization, when required, should be scheduled **no sooner than 10 days after the subject's prior dose**, even if this requires an unscheduled visit. If a subject has a visit that is scheduled less than 10 days after the last dose, the visit procedures may take place, but lipid, ADA, PK, and PCSK9 testing should be postponed and performed at the earliest possible time, at an unscheduled visit, no sooner than 10 days after the subject's last dose. A lipid profile will not be collected at EDC/EOS visits. ADA, PK, and PCSK9 samples will be collected at EDC/EOS visits.

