#### **7.2.7.2. Hypersensitivity Types 1 and 3 Reactions**

Type 1 hypersensitivity or allergic (eg, shortness of breath, urticaria, anaphylaxis, angioedema) reactions are theoretically possible in response to any injected protein. Immune complex mediated Type 3 hypersensitivity reactions are similar to the adverse events (AEs) of Type 1 reactions but are likely to be delayed from the time of injection and may include symptoms such as rash, urticaria, polyarthritis, myalgias, polysynovitis, fever, and, if severe, glomerulonephritis.

In the case of a hypersensitivity reaction, the subject will be treated symptomatically with supportive care, further monitoring, and treatment with anti-histamines and/or corticosteroids. Study injections may be stopped and the subject will be followed until the end of the study. At the time of any hypersensitivity reaction an ADA, PK, and PCSK9 specimen should be collected, and another sample collected at the next visit, as per the [Schedule of Activities](#).

If a subject reports an injection site reaction that has not resolved by the end of the third day, after dosing, an unscheduled visit should be performed, to collect an ADA, PK, and PCSK9 sample.

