8.2.4.5. Injection Site Adverse Events

Injection site adverse events will be summarized by ADA status (positive, negative) and by nAb status (positive, negative). The higher level term of “injection site reactions” will be used to identify the adverse events.

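### Reaction-triggered antibody samples count toward ADA and nAb status, so the reaction-by-status tables lean toward an association; a scheduled-samples-only version should be shown beside them.

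*SAP*

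**What the plan says.** Scheduled post-dose ADA draws are sparse. Protocol 6.4.2 to 6.4.4 place them at Visits 6, 8, 10, 12, 14, 17 and 20 and at EDC/EOS.

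Protocol 7.2.7.2 adds two reaction-driven draws. For hypersensitivity: "At the time of any hypersensitivity reaction an ADA, PK, and PCSK9 specimen should be collected, and another sample collected at the next visit". For injection site reactions: "If a subject reports an injection site reaction that has not resolved by the end of the third day, after dosing", then "an unscheduled visit should be performed, to collect an ADA, PK, and PCSK9 sample". The protocol's Document History lists the injection site rule among the Amendment 2 changes (12 February 2016).

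SAP 8.2.4.1.1 classes a subject as ADA-positive if "The subject is ADA negative at baseline and has at least 1 ADA positive post-dose measurement". A missing baseline is handled the same way. A subject positive at baseline needs a titer rise above 1.58 log2 units in at least one post-dose sample. A baseline-negative subject is ADA-negative only if every post-dose sample is negative. The nAb rules run in parallel. None of them separates scheduled from triggered samples.

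SAP 5.4.2.2, 8.2.3, 8.2.4.4 and 8.2.4.5 then tabulate adverse events, serious adverse events and injection site adverse events by ADA and nAb status in bococizumab subjects. SAP 8.2.4.1 says that placebo samples are not assayed.

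**The concern.** Having the reaction buys extra antibody tests, and one positive test is enough to change column. Subjects with reactions are thus more likely to be classed positive even when antibodies have nothing to do with reactions. The reaction rate goes up in the positive column and down in the negative column. This happens at equal follow-up, so it is distinct from any effect of longer observation.

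SAP 8.2.3 makes hypersensitivity reactions and injection site events Tier 1 events, and the tables by antibody status exist to show whether antibodies accompany them. A procedure that leans toward yes weakens that reading. With no placebo assays, no comparison within the trial would expose the artefact. The fields named for the SAP 8.2.4.2 listing do not mark a sample as triggered.

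**Working it through.** **Inputs from the documents.** ADA incidence in three earlier studies is 201/473 = 42.5% (Protocol 1.2.3), which reproduces. Scheduled draws fall at Weeks 4, 14 and 40 (Visits 6, 8, 10). The documents give no figure for the association itself.

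**Assumptions.** Follow-up of 56 weeks with an end-of-study draw then; four scheduled samples giving 42.5% ever positive; a constant weekly onset probability a and reversion probability b; reactions independent of antibodies; one extra sample at a random week; 5% or 10% of subjects reacting.

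**Step 1: calibrate.** For a subject negative at the last sample, the chance of being positive g weeks later is a/(a+b) × [1 − (1−a−b)^g]. With b = 5%, a = 1.504% fits: a/(a+b) = 0.2312 and 1−a−b = 0.93496. The gaps of 4, 10, 26 and 16 weeks give chances 0.0545, 0.1132, 0.1909 and 0.1524. All four samples are negative with probability 0.9455 × 0.8868 × 0.8091 × 0.8476 = 0.575, so 42.5% are ever positive.

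**Step 2: add one sample.** Inserting one draw and averaging over Weeks 1 to 56 raises the chance of ADA-positive status, q, to 44.4% at b = 5% and 47.1% at b = 20%.

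**Step 3: turn q into table rates.** With reaction proportion r, the rate is rq/[rq + (1−r)(0.425)] in the positive column and r(1−q)/[r(1−q) + (1−r)(0.575)] in the negative column. At b = 20% and r = 5%: 0.02357/0.42732 = 5.52% and 0.02643/0.57268 = 4.62%, a ratio of 1.20.

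**Step 4: dilute.** SAP 8.2.4.5 covers all injection site events, but only prolonged ones trigger a draw. If 30% of reactors are sampled, q becomes 0.425 + 0.3 × (q − 0.425).

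| Weekly reversion | q, one extra sample | Ratio, every reactor sampled (r = 5%) | Ratio, 30% sampled (r = 10%) |
|---|---|---|---|
| 0 | 42.5% | 1.00 | 1.00 |
| 1% | 42.9% | 1.02 | 1.00 |
| 2% | 43.3% | 1.03 | 1.01 |
| 5% | 44.4% | 1.07 | 1.02 |
| 10% | 45.7% | 1.13 | 1.04 |
| 20% | 47.1% | 1.20 | 1.05 |

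**Cross-check with a different model.** A beta-binomial model with five scheduled samples, still 42.5% ever positive, and one extra gives q = 48.5%, 45.6%, 44.2% and 43.0% at within-subject correlations of 0, 0.3, 0.6 and 0.9. The odds ratios against 42.5% are 1.28, 1.14, 1.07 and 1.02. At correlation 0.3 with 10% reacting, the table ratio is 1.12 if all reactors are sampled and 1.04 if 30% are. Direction and size agree.

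**With scheduled samples only,** q is 42.5% for reactors and non-reactors alike under the null, and the ratio is 1.00.

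**The case against.** The best defence is that the effect is small, already qualified, and costly to remove. SAP 5.4.2.2 and 5.4.2.3 advise caution with subgroups formed after randomization, SAP 8.2.3 calls safety analyses exploratory, and no p-value is specified for these tables. No document gives a reversion rate, and with persistent antibodies the ratio is essentially 1. Dropping triggered samples would also discard the draw closest to the reaction. If the weekly reaction hazard were truly three times higher while ADA-positive (an assumption), scheduled-only status would class about 11-34% of subjects who were positive at their reaction as negative. The table ratio would fall from about 1.8 to between about 1.6 and 1.2.

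Most of this stands on size and on the remedy. It does not remove the mechanism: the SAP's caution is general and says nothing about sampling driven by the outcome.

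A reader might infer more than the documents support:
- **That any single positive sample makes anyone ADA-positive.** Baseline-positive subjects need the 1.58-unit rise, although one triggered sample can supply it.
- **That the injection site trigger began only with Amendment 2.** The Document History says that the sampling rules were modified so that "anti-drug antibody measurements would be obtained for an injection site reaction that lasts more than 3 days". The text that this replaced is not available. If the rule did begin then, it ran for at most 263 days, to 01 November 2016.
- **That triggered draws are often within 10 days of a dose.** Footnote 1 to the Schedule of Activities says "ADA, PK, and PCSK9 testing, after randomization, when required, should be scheduled" at least 10 days after dosing, even at an unscheduled visit. Protocol 7.2.7.2 fixes no day for the injection site draw. Nor do the documents say that an early draw is more often positive.
- **That ratios of 1.33 or 1.69 are realistic.** These need uncorrelated successive samples: 1 − (1−p)^4 = 0.425 gives p = 0.129, hence 49.9% positive with five samples and 56.3% with six. That sits badly with the SAP's persistent-response class of at least 16 weeks. The larger figure also needs two extra samples. An injection site reaction triggers one, and the second hypersensitivity draw is extra only if the next visit has no ADA draw scheduled.

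**Conclusion.** The concern holds as an avoidable bias in descriptive safety tables. The protocol orders the extra samples, the SAP counts them, and the same reactions are tabulated by the resulting status without separating them.

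Under no true link, the ratio is inflated by about 7-20% where every reactor is sampled once and weekly reversion is 5-20%; this is closest to the hypersensitivity rows. In the all-injection-site table it is about 2-5% if 30% of reactors trigger a sample. It is near zero if antibodies largely persist. The reversion rate, the reaction rates and the shares sampled are all assumed. The SAP's own transient-response class shows that it expects some reversion.

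The documents do not support the stronger conclusion that the any-sample status is wrong and must be replaced, since each definition can mislead in its own direction. Primary and key secondary analyses are unaffected.

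**What to change.** Keep the planned any-sample status in SAP 8.2.4.1.1. For hypersensitivity and injection site adverse events by ADA and nAb status, add a parallel version with status derived from scheduled samples only. Draws postponed under the 10-day rule and EDC/EOS draws count as scheduled; reaction-triggered draws do not.

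Also:
- flag reaction-triggered samples in the SAP 8.2.4.2 listing;
- report the number of ADA samples per subject by reaction status;
- state that the two versions are to be read together, because the any-sample version can overstate an association and the scheduled-only version can understate one.

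The cost is a sample flag, a short addition to the SAP and a few more descriptive tables. No data are dropped.

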  - **IRT interaction:** At the time of the visit, the visit will be registered in the IRT which will trigger an allocation of investigational product for the subject.
  - **Investigational product:** Dispense investigational product based on IRT randomization code. If there is dosing during the visit, subjects will be observed, at the visit, during the injection of investigational product, either by self-injection, or as performed by a care giver, after all other procedures have been completed.
  - Subjects will be provided with investigational product kits to bring home with them and will be reminded about storage conditions.
  - **Compliance check:** The subject's compliance with investigational product administration, as described in [Section 5.3](#) will be assessed. Subjects will be instructed to bring any used and unused syringe cartons to each visit. Used syringes will be returned to the study center in a biohazard container, when it is full, to receive a new container, and when directed by the study site, as described in [Section 5.3](#). Compliance with lifestyle guidelines should also be reviewed ([Section 4.4](#)) and recorded in the CRF.
  - **Contraception check:** A contraception check should be made for male and female subjects, who, with their partner, are of childbearing potential ([Section 4.4.2](#)).

The following laboratory tests should be collected:

- Blood for fasting lipid profile:  
  
Lipid level tests should be scheduled no sooner than 10 days after the subject's prior dose, even if this requires an unscheduled visit;  
  
If a subject has a visit that is scheduled less than 10 days after the last dose, the visit procedures may take place, but lipid testing should be postponed and performed at the earliest possible time, at an unscheduled visit, no sooner than 10 days after the subject's last dose;
- Special lipid and efficacy studies, as described in [Section 7.1.2.2](#), will be collected at Week 14, Visit 8.
- Chemistry group;
- LFTs;

- Blood specimens acquired for ADA, bococizumab level (PK), and PCSK9 level in all subjects at Visits 8, 10, and 12;  
After randomization, if lipid sampling has been postponed to an unscheduled visit, the corresponding ADA/PK/PCSK9 samples should be postponed as well, and collected at the same time as the rescheduled lipid sample collection;
- Urine and serum for pregnancy testing (if indicated).

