- **IRT interaction:** At the time of the visit, the visit will be registered in the IRT which will trigger an allocation of investigational product for the subject, except at the EDC or EOS visit. At the EDC or EOS visit, the EDC or EOS status will be registered.
- **Investigational product:** Dispense investigational product based on IRT randomization code (except for EDC or EOS visit). If there is dosing during the visit, subjects will be observed, at the visit, during the injection of investigational product, either by self-injection, or as performed by a care giver, after all other procedures have been completed. Except for EDC or EOS visit, subjects will be provided with investigational product kits to bring home with them and will be reminded about storage conditions.
- **Compliance check:** The subject's compliance with investigational product administration, as described in [Section 5.3](#), will be assessed. Subjects will be instructed to bring any used and unused syringe cartons to each visit. Used syringes

will be returned to the study center in a biohazard container, when it is full, to receive a new container, and when directed by the study site, as described in [Section 5.3](#). Compliance with lifestyle guidelines should also be reviewed ([Section 4.4](#)) and recorded in the CRF.

- **Contraception check:** A contraception check should be made for male and female subjects, who, with their partner, are of childbearing potential ([Section 4.4.2](#)).

The following laboratory tests will be collected:

- Blood for fasting lipid profile:

Lipid level tests should be scheduled no sooner than 10 days after the subject's prior dose, even if this requires an unscheduled visit;

If a subject has a visit that is scheduled less than 10 days after the last dose, the visit procedures may take place, but lipid testing should be postponed and performed at the earliest possible time, at an unscheduled visit, no sooner than 10 days after the subject's last dose;

A lipid profile will not be collected at EDC/EOS visits;

- Special lipid and efficacy studies as described in [Section 7.1.2.2](#), at Week 52, Visit 11;
- Biospecimens as described in [Section 7.5](#), at Week 52, Visit 11;
- Chemistry group (including LFTs and CK level);
- Hematology;
- Urinalysis;
- HbA1c for all subjects at Visit 11 and EDC and/or EOS;
- Blood specimens acquired for ADA, bococizumab level, and PCSK9 level in all subjects at Visits 14, 17, 20, and EDC or EOS;

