2.1. Study Design

This is an event driven, Phase 3 multi-center, double-blind, randomized parallel group evaluation of the efficacy, safety, and tolerability of bococizumab compared with placebo, in reducing the occurrence of major cardiovascular (CV) events in subjects at risk, who are on background lipid lowering treatment and have an LDL-C \geq 70 mg/dL (1.81 mmol/L) or non-HDL-C \geq 100 mg/dL (2.59 mmol/L). After obtaining informed consent, there will be a pre-screening visit. At this visit subjects will have consented to have had lipid levels assessed and to provide medical records for review, only, so as to determine if the subject qualified for this study. If qualified, [t]he interactive response technologies (IRT) system will determine if the subject is eligible for the study or if the subject should be screen failed. This will be followed within 30 days, by a screening visit, and a run-in period of up to 6 weeks, during which subjects will be fully assessed with respect to the trial enrollment criteria and compliance with the self-administration of subcutaneous injections. The run-in period will be followed by the treatment period, the duration of which will be determined by the number of subjects with primary endpoint events, and concluded by a safety follow-up period, as illustrated in the schematic below (Figure 1).

Figure 1 B1481022 Study Diagram

The End of Study (EOS) will be announced to study sites, when the Sponsor estimates that criteria for stopping the study in Section 3 of the protocol have been satisfied. EOS visits should be scheduled as soon as possible, after that announcement. The EOS visit should occur no sooner than 14 days after the last dose of investigational product (IP) was administered for subjects taking IP. If the EOS visit has taken place earlier than 40 days after the last dose of IP administration, subjects will receive a telephone call to determine if any serious adverse events have taken place. All EOS procedures should be done for all randomized subjects when the study is completed, whether or not the subject is taking double-blind investigational product.

Approximately 85,000 subjects may be screened and approximately 17,000 subjects will be randomized. Subjects will be randomized to bococizumab 150 mg or placebo Q2wks in a 1:1 ratio. Randomization will be stratified by geographic region and LDL-C at the pre-screening visit (<100 mg/dL, ≥100 mg/dL).

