Observed values and changes from baseline in systolic BP, diastolic BP, PR, and weight will be tabulated by visit as continuous endpoints according to sponsor standards. Height, waist circumference, and temperature will be listed.

Anti-drug antibody (ADA) and neutralizing antibody (nAb)

The number of samples analyzed for ADA and nAb will be summarized.

ADA and nAb status will be summarized as categorical endpoints by visit and overall at the subject level. The numbers and percentages of ADA positive and nAb positive subjects classified according to timing of first result with respect to last dose of bococizumab (on treatment/off treatment) and characterization of ADA and nAb response (treatment induced/treatment boosted/indeterminate) using the definitions in [Section 6.2](#) will be presented.

In addition, the summary of nAb will be repeated with two different denominators: number of non-missing ADA samples and number of ADA positive subjects.

Antibody titers for ADA positive subjects and nAb positive subjects will be summarized by visit as continuous endpoints. Boxplots of ADA titer and nAb titer over time will be presented.

Time to first positive ADA result and time to first positive nAb result will be summarized as continuous endpoints in the subgroups listed [Section 5.4.2.5](#).

Clinical laboratory measurements

Observed values and changes from baseline in hematology, blood chemistry, and quantitative urinalysis parameters will be tabulated by visit as continuous endpoints according to sponsor standards. Mean changes from baseline will be plotted longitudinally for selected laboratory parameters including creatine kinase, hemoglobin, HbA1c and glucose, according to sponsor standards. Qualitative urinalysis parameters will be listed.

Observed value and change from baseline in HbA1c will be tabulated by visit as continuous endpoints for the subgroup identified in [Section 5.4.2.3](#).

Laboratory shift tables for hemoglobin, CK, glucose, and HbA1c will summarize shifts from baseline status (below lower limit of normal, normal, above upper limit of normal) to post-baseline status at each scheduled measurement. Shifts from baseline to the smallest post-baseline and largest post-baseline measurement will also be tabulated. These shift tables will also be done for the subgroups identified in [Section 5.4.2.3](#).

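### The on-/off-treatment antibody split dates onset by the first positive sample, so a first positive at the end-of-study visit is labelled off-treatment even when most of the possible onset interval was on drug

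*SAP*

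**What the plan says.** SAP Section 8.2.4.1.1 divides ADA-positive and nAb-positive subjects by timing. The on-treatment rule is "The subject has any ADA (nAb) detected within ≤ 14 days after last dose". The off-treatment rule is "The subject has their first ADA (nAb) detected >14 days after last dose". SAP Section 8.2.3 also keys the split to the first result relative to the last bococizumab dose. No rule refers to the last negative sample. An indeterminate class exists for response type and for duration of response, but not for timing.

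SAP Section 2.1 sets the earliest final visit: "The EOS visit should occur no sooner than 14 days after the last dose of investigational product (IP) was administered for subjects taking IP". Protocol Sections 3 and 6.4.4 give the same 14-day minimum. An ADA sample is drawn at early-discontinuation (EDC) and EOS visits.

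Scheduled ADA samples are at baseline, at Visit 6 (Protocol Section 6.4.2), then "PCSK9 level in all subjects at Visits 8, 10, and 12" (Protocol Section 6.4.3) and "PCSK9 level in all subjects at Visits 14, 17, 20, and EDC or EOS" (Protocol Section 6.4.4). Visit 11 (Week 52) has none. Protocol Section 7.2.7.2 adds samples for hypersensitivity reactions and for injection-site reactions that have not resolved by the end of the third day.

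**The concern.** The rule uses the date of detection to decide whether an antibody belongs to the treatment period. With sparse sampling, the first positive shows only that the antibody appeared at some point since the last negative sample. For a subject dosed until the trial closes, the last sample is the EOS sample, which by design falls on or after the day on which the on-treatment window ends. A first positive there goes into the off-treatment row almost by construction, wherever the onset lay.

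Immunogenicity is a stated safety objective, and a reader of the table will naturally take off-treatment antibodies to mean antibodies that arose after the drug was stopped. The table as defined cannot support that reading.

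**Working it through.** **Inputs.** Post-dose ADA sampling is at Weeks 4, 14, 40, 70, 104, 156 and 208, plus EDC/EOS (Protocol Sections 6.4.2 to 6.4.4 and the Schedule of Activities). The on-treatment window is 14 days (SAP 8.2.4.1.1). The earliest EOS for subjects on drug is day 14 (SAP 2.1). The longest dosing interval is 28 days, after a second dose adjustment (Protocol Section 5.4.1.1). The documents give no actual EOS dates, so days 15 and 40 after the last dose are assumed here as illustrations.

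**Step 1: sample gaps.** 4−0 = 4, 14−4 = 10, 40−14 = 26, 70−40 = 30, 104−70 = 34, 156−104 = 52 and 208−156 = 52 weeks.

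**Step 2: where an EOS sample falls.** Day 14 exactly counts as on-treatment. From day 15 a first positive counts as off-treatment.

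**Step 3: how much of the possible onset interval was on drug.** For a first positive at EOS, on-drug share = (interval − lag) / interval, where the interval runs from the last negative sample to EOS and the lag is the time from last dose to EOS. For a 30-week interval (210 days), day 15 gives (210 − 15)/210 = 93% and day 40 gives (210 − 40)/210 = 81%.

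| Interval since last negative | EOS day 15 | EOS day 40 |
|---|---|---|
| 4 weeks | 46% | 0% |
| 10 weeks | 79% | 43% |
| 26 weeks | 92% | 78% |
| 30 weeks | 93% | 81% |
| 34 weeks | 94% | 83% |
| 52 weeks | 96% | 89% |

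These rows use full scheduled gaps. An EOS visit part-way through a gap leaves a shorter interval and a lower share. The share exceeds one half whenever the interval is longer than twice the lag: 30 days for a day-15 EOS, 80 days for a day-40 EOS.

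**Step 4: average over EOS times.** Assume EOS is uniform from Week 15 to an end between Week 60 and Week 160, with lags of 15 to 40 days. The on-drug share averaged over subjects is then 42% to 76%. Total on-drug time divided by total time since the last sample is 57% to 89%. The second figure also assumes that a first positive at EOS becomes more likely in proportion to interval length.

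**Step 5: reach of the longest gap.** From the original protocol date (26 August 2013) to the program stop (1 November 2016) is 166 weeks. The 52-week gap therefore concerns only subjects randomized more than 104 weeks before the stop; the others have scheduled gaps of at most 34 weeks.

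**Step 6: subjects on 4-weekly dosing.** A first positive on days 15 to 28 after the final dose is called off-treatment although one dosing interval has not yet elapsed.

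**The case against.** The strongest reply is that the SAP describes detection, not onset. The paragraph concerns the timing of a positive measurement, and both rules speak of detection. Read literally, the label is correct. That stands as a reading of the text, but the resulting category is a subject having off-treatment antibodies, and nothing in the table tells the reader how wide the onset interval is.

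Second, a reader might infer that the rule hides treatment-induced antibodies or understates overall immunogenicity. The documents do not support that. Treatment-induced status requires a negative baseline (or, if baseline is missing, an earlier negative post-dose sample) and any later positive, with no 14-day limit. Subject-level ADA and nAb status, overall incidence, and the adverse-event, LDL-C and laboratory summaries by that status do not use the cut.

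Third, some of the missing information is already planned. SAP Section 8.2.4.3 lists ADA and nAb status by subject and visit for ADA-positive subjects, and time to first positive is summarized. This helps, but neither listing names the last-dose date or the last-negative sample date.

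Fourth, the affected group has limits. Subjects with an earlier on-drug positive are classified correctly. The 14-day minimum is set for EOS, not EDC, where ADA testing need only wait 10 days after the prior dose. Early discontinuers who stay in the study give further samples. Triggered samples shorten some gaps. The 4-weekly point concerns few subjects: Protocol Section 1.2.6 predicts 1.7% (LDL-C below 100 mg/dL) and 0.4% (100 mg/dL or above) reaching that schedule. All of this stands.

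It is also tempting to say that stopping the program made the problem worse. The documents do not show this: at planned completion too, subjects stop dosing and attend EOS at least 14 days later.

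**Conclusion.** The point holds as a defect in one descriptive split. Applied exactly, the rule puts every first positive at an EOS sample drawn after day 14 into the off-treatment row, including cases where most of the possible onset interval was on drug. The shares above are calendar arithmetic with assumed EOS days. Reading them as the probability that an antibody arose on drug further assumes that onset is uniform over the interval. They apply only to subjects whose first positive is at EOS, and the documents give no means of counting those. No fixed proportion of mislabelled subjects should therefore be quoted. No test, alpha allocation or efficacy conclusion depends on the split.

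**What to change.** In SAP Section 8.2.4.1.1, define the on-treatment window as one dosing interval after the last dose: 14 days for subjects on the 2-weekly schedule and 28 days for those moved to the 4-weekly schedule. Then:

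- Report a subject as off-treatment only when a negative sample was taken after that window closed and a later sample is positive.
- When the first positive falls after the window and the last negative was taken before the window closed, report it in a separate row, such as *first detected after last dose; onset timing undetermined*. Do not count it as on- or off-treatment. Moving all such cases to on-treatment would only reverse the bias.
- Add the last-negative sample date and the last-dose date to the ADA listing in SAP Section 8.2.4.2.
- Correct the pointer in SAP Section 8.2.3, which sends the reader to Section 6.2 for definitions that stand in 8.2.4.1.1.

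The cost is a change of wording and one derived variable from sample and dosing dates already collected. The downside is that few subjects will remain in the off-treatment row.
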